6.6.2. Safety Variable Definitions

Compliance

% Compliance = percentage of study drug actually taken compared to what was expected based on the planned dose in time period i (where subject is receiving a constant dose), calculated as follows:

$$\%Compliance_i = 100 \times \left(\frac{\# \text{ Dispensed} - \# \text{ Returned}}{\# \text{ Dispensed} - \# \text{ Expected Returned}} \right)_i$$

Treatment Emergent Adverse Events

Adverse events (AEs) are recorded from signing of the informed consent form through the final follow-up assessment.

Adverse events observed prior to first dose are non-treatment emergent.

Treatment emergent adverse events are events with a start date/time after the first dose date/time until the last dose date/time plus the protocol defined follow-up period, 30 days.

Adverse events observed after the last dose and after the follow-up period are non-treatment emergent.

Only treatment-emergent AEs will be summarized in the tables.

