6.7.3. Missing Start and Stop Dates for Adverse Events

Missing start date and times will be handled as follows:

- AE onset date completely missing:
 - If AE is not ongoing and AE onset date missing and AE end date missing, then impute AE onset as date/time of first dose.
 - Else if AE is not ongoing and AE onset date missing and AE end date not missing and date/time of first dose \leq AE end date, then impute AE onset as date/time of first dose of study drug.
 - Else if AE is not ongoing and AE onset date missing and AE end date not missing and AE end date is BEFORE first dose of study drug, then impute AE onset as AE end date YEAR and MONTH with 01 as the day and 00:00 as time.
 - Else if AE IS ongoing and AE onset date missing, then impute AE onset as date/time of first study drug dose.
- AE onset date has year and month only:
 - If AE onset date has year and month only and they are the year and month of first dose of study drug, then impute AE onset as date/time of first dose:
 - Else if AE onset date has year and month only and date/time of first dose is not missing, then impute AE onset as AE onset year and month with 01 as the date and 00:00 as the time.
- AE onset date has year only:
 - If AE onset date has year only and it is year of first dose of study drug, then impute AE onset as date/time of first dose of study drug.
 - Else if AE onset date has year only and date of first study drug dose is not missing and year of AE onset is NOT the year of first dose of study drug, then impute AE onset as Jan. 1 of the AE onset year and 00:00 as the time.
- AE onset missing (where it was not handled by the above cases):
 - If AE onset date is missing, then impute AE onset as date/time of first study drug dose.
- AE onset has complete date but missing time:
 - If AE onset date is a date only and is same as date of first study drug dose, then impute AE onset as date/time of first study drug dose.
 - Else if AE onset date is a date only and is NOT = date of first study drug dose, then impute AE onset as AE onset date with 00:00 as the time.

Missing end date and times will be handled as follows:

- AE end date - completely missing:
 - If AE is not ongoing and both AE onset and AE end dates are missing, then impute AE end date as date/time of last study drug dose.
 - Else if AE is not ongoing and AE onset date not missing and AE end date missing AND AE onset date \leq date/time of last dose, then impute AE end date as date/time of last study drug dose.

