8.1. Adverse Event Preferred Term and Body/Organ System Summary Tables

Adverse events will be coded to the preferred terms of the Medical Dictionary for Regulatory Activities (MedDRA®). Summaries will present by system organ class (SOC), preferred term (PT) and severity and/or relatedness, the frequency and percentage of subjects reporting each observed event.

A treatment-emergent adverse event (TEAE) will be defined as any AE that begins on or after the date of first dose of study drug up to the date of last dose of study drug plus the number of days in the follow-up period. AEs observed during the period from obtaining informed consent to the start of administration of study drug will be regarded separately from TEAEs.

All AEs and all TEAEs will be listed by subject.

Subjects who experienced treatment-limiting AEs will be listed. Treatment-limiting AEs are defined as any event that leads to permanent or temporary discontinuation from treatment, or a reduction in the treatment dose.

Summary of adverse events will be dependent on adverse events observed. If no adverse events meeting a specific table are observed, the summary table will not be completed. Blank summary tables will not be utilized.

The following is the list of adverse event tables:

Overall:

- Overall Summary of Adverse Events

Label	Reporting Format
Adverse Event	F
Moderate or Severe Adverse Event	F
Adverse Event Related to Study Drug	F
Moderate or Severe Adverse Event Related to Study Drug	F
Serious Adverse Event	F
Serious Adverse Event Related to Study Drug	F
Adverse Events Leading to Permanent Study Drug Discontinuation	F
Adverse Events Leading to Temporary Interruption of Study Drug	F
Death During Study	F

By preferred term:

- Treatment-emergent Adverse Events by PT
- Treatment-emergent Adverse Events by SOC and PT

By severity:

- Treatment-emergent Adverse Events by SOC, PT and Severity
- Serious Adverse Events
- Deaths during Study

By relatedness:

- Drug-Related Treatment-emergent Adverse Events by SOC and PT
- Drug-Related Treatment-emergent Adverse Events by SOC, PT and Severity
- Drug-related Serious Adverse Events

Other:

- Adverse events leading to premature study drug discontinuation

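### SAP 6.6.2 starts a TEAE strictly after the first dose, yet 7 of the 11 onset-imputation rules in SAP 6.7.3 put the onset exactly at the first dose, where SAP 8.1 and the protocol count it

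*SAP*

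**What the plan says.** The SAP defines a TEAE twice.

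- **SAP 6.6.2** works in date/time: "Treatment emergent adverse events are events with a start date/time after the first dose date/time until the last dose date/time", extended by the 30-day follow-up. The complementary class at the start is "Adverse events observed prior to first dose are non-treatment emergent". The section closes with "Only treatment-emergent AEs will be summarized in the tables".
- **SAP 8.1**, which specifies the AE tables, works in dates: "any AE that begins on or after the date of first dose of study drug". Its next sentence adds "AEs observed during the period from obtaining informed consent to the start of administration of study drug will be regarded separately from TEAEs".

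Protocol 8.2.1 is inclusive: an AE arising while the first dose is being given, or later, counts until 30 days after the final dose. Protocol 9.3.5 sets apart only the AEs that precede the first dose. Protocol 8.2.1 and 8.2.4 require the onset time for AEs on the first-dose date.

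SAP 6.7.3 imputes incomplete onsets, often to the first dose itself. Two examples are "Else if AE IS ongoing and AE onset date missing, then impute AE onset as date/time of first study drug dose" and, for a complete date without a time, "If AE onset date is a date only and is same as date of first study drug dose, then impute AE onset as" the first-dose date/time.

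SAP 5.1.1 lists three departures from the protocol's analyses (acne and hirsutism, semen, menstrual cyclicity). None concerns the TEAE definition.

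**The concern.** On continuous clock time, the difference between *after* and *at or after* would almost never matter. Here it does, because the imputation rules produce exact ties with the first-dose time. Under 6.6.2 a tied AE is in neither class. Since only treatment-emergent AEs are tabulated, a programmer who codes 6.6.2 as written drops it from the tables. One who codes 8.1 keeps it.

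AEs belong to the primary (safety) endpoint. The SAP 11.3 index has 11 tables numbered 14.3.3. Ten are titled as treatment-emergent, including those for serious, drug-related and discontinuation AEs; the exception is the table of deaths within 28 days. The index also has one listing for TEAEs (16.2.7.1) and one for non-TEAEs (16.2.7.5), so an AE in neither class has no defined place in that pair.

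**Working it through.** The documents give no figure to reproduce on this point. The check is to go through every onset rule and test the result against each definition.

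**Inputs.** Let *t0* be the first-dose date/time and *t* the onset after imputation. The rules are those in SAP 6.7.3, in order.

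| Rule | What is known | Imputed onset | Tie with *t0*? |
|---|---|---|---|
| 1 | Onset and end missing, not ongoing | *t0* | yes |
| 2 | Onset missing, end at or after first dose | *t0* | yes |
| 3 | Onset missing, end before first dose | Day 1 of the end month, 00:00 | no |
| 4 | Onset missing, ongoing | *t0* | yes |
| 5 | Year and month, same as first dose | *t0* | yes |
| 6 | Year and month, different | Day 1 of that month, 00:00 | no |
| 7 | Year only, same as first dose | *t0* | yes |
| 8 | Year only, different | 1 January, 00:00 | no |
| 9 | Missing, not handled above | *t0* | yes |
| 10 | First-dose date, no time | *t0* | yes |
| 11 | Another date, no time | That date, 00:00 | no |

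**Count.** Rules: 4 (completely missing) + 2 (year and month) + 2 (year only) + 1 (residual) + 2 (date without time) = 11. Ties: 3 + 1 + 1 + 1 + 1 = 7.

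**Classification of a tie, *t* = *t0*.**

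- 6.6.2, treatment-emergent (*t* > *t0*): false, so 0 of 7 rules qualify.
- 6.6.2, non-treatment-emergent (*t* < *t0*): also false, so the AE is unclassified.
- 8.1, first sentence (onset date ≥ first-dose date): true. The second sentence does not remove it, because the onset does not precede the start of administration. 7 of 7 qualify.
- Protocol 8.2.1 (*t* ≥ *t0*): true, 7 of 7.

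**The other four rules.** Rule 3 puts the onset before an end date that itself precedes the first dose, so *t* < *t0*. Rules 6, 8 and 11 apply only when the month, year or date differs from that of the first dose, so *t* cannot equal *t0*. Their class is the same under > and ≥. An inclusive bound therefore agrees with 8.1 (both sentences together) in 11 of 11 rules, and the strict bound in 4 of 11.

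**What the imputation assumes.** When the onset is missing and an end date is known, the only condition that gives a pre-dose onset is "AE end date is BEFORE first dose of study drug". Section 6.7.3 thus works with an inclusive boundary.

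**A second mismatch, on Day 1.** The protocol's initial regimen is dosed at 10pm, with visit samples at 8am. Take a 10pm first dose and recorded onset times:

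| Day 1 onset | 6.6.2 | 8.1, first sentence alone | Protocol 8.2.1 |
|---|---|---|---|
| 8am | no | yes | no |
| Imputed to 10pm | unclassified | yes | yes |
| 11pm | yes | yes | yes |

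Changing 6.6.2 alone would correct the middle row but leave the first, so 8.1 also has to move to date/time.

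**The case against.** The best reply is that the intent is clear. The protocol definition is inclusive and 5.1.1 declares no change to it. Section 8.1 is inclusive too, 6.6.2 labels only AEs before the first dose as non-treatment-emergent, and imputing to the first dose has little purpose unless the AE is then counted. A careful programmer would probably use ≥. This is fair, and it supports the proposed wording. It does not remove the conflict: 6.6.2 states a strict rule, ties it to what enters the tables, and is not ranked below the other definitions.

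A second reply concerns weight. The 7 of 11 counts rules, and rule 9 is a catch-all with little left to catch. AEs are reviewed at every visit from first dosing and Day 1 onset times are required, so few AEs should need imputation. Section 8.1 has all AEs listed by subject, and the discontinuation, serious-AE and death listings (16.2.7.2 to 16.2.7.4) are not restricted by title to TEAEs. AE incidence is, in general, not formally tested. All of this stands and limits the likely effect. It does not settle which AEs enter the treatment-emergent tables.

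Third, the Table 4 row for AEs also covers ECGs and laboratory data, and its wording does not say whether the bound is inclusive. That is correct. Table 4 is a place to align and is not itself evidence of conflict.

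**Conclusion.** The concern holds. Two SAP definitions of the primary-endpoint class give different answers for an onset that the SAP's own imputation creates in 7 of 11 rules, and one of them departs from the protocol without being declared as a change. Read literally, 6.6.2 leaves such an AE out of the tables.

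The size in events is unknown and may be zero, and no shift in incidence is claimed. As a scale only: the final sample size in SAP 4.3 is 11, so if all 11 were dosed, one subject moving into or out of a table row would change it by 1/11, about 9 percentage points.

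The conclusion rests on reading *after* in 6.6.2 in its ordinary strict sense, and on reading the second sentence of 8.1 as refining the first. The correction should be made, but it is one of wording and does not call the design into question.

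**What to change.** Use one definition in SAP 6.6.2, Table 4 and 8.1: a TEAE is an AE with onset date/time at or after the first-dose date/time, through the last dose plus 30 days. Add two statements:

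- An onset imputed to the first-dose date/time counts as treatment-emergent.
- For AEs on Day 1, the collected onset time is used where there is one.

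In Table 4 the change concerns AEs only. Split the row if needed, so that the ECG and laboratory bound stays as it is.

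The cost is wording edits in three places, with no new data. Relative to 6.6.2, TEAE counts can only stay the same or rise. Relative to the first sentence of 8.1 taken alone, Day 1 AEs with a recorded pre-dose time would drop out, as the protocol and the next sentence of 8.1 intend.

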## 1.2 Schema

### 1.3 Schedule of Activities

	Screening Period	Treatment Period								Follow-up/ET
		1  Screening	2 Baseline	3	4	5	6	7	8	
VISIT NUMBER		0	2	4	6	8	10	12	16	
STUDY WEEK										
STUDY DAY 	12 weeks before Day 1	1	15	29	43	57	71	85		Last dose +30 days
Site Visits 	X	X		X		X		X	X	
Home Visits 			X		X		X			
Informed consent	X									
Inclusion/exclusion criteria	X	X								
Demography 	X									
Medical history 	X									
Prior medications 	X									
Concomitant medications 	X	X	X	X	X	X	X	X	X	

 For subjects rolling over from Study SPR001-201, the final safety follow-up visit of Study SPR001-201 may coincide with the screening visit of this study (with any overlapping assessments conducted only once). If a subject completed the final follow-up visit of Study SPR001-201 ≤3 months before the screening period of this study, overlapping assessments conducted at that final follow-up visit need not be repeated at screening for this study. If a subject completed the final follow-up visit of Study SPR001-201 >3 months before the screening period of this study, all screening assessments must be conducted anew, including some additional screening assessments specified for such subjects.

 All visits should be performed on the indicated study days. In cases where this is not possible, the following visit windows apply: ±3 days for Visits 3 to 8 and ±7 days for the safety follow-up visit (Visit 9). All visits, including the early termination visit, should be scheduled for the morning, to accommodate 8am laboratory assessments.

 Study visits for screening; at Weeks 0, 4, 8, and 12; and at final follow-up must be conducted as in-clinic outpatient visits.

 Study visits at Weeks 2, 6, and 10 may be conducted as either in-clinic outpatient visits or in-home visits by qualified study personnel.

 Demographic information needs to be collected only for SPR001-naïve subjects.

 Full medical history and prior medications from the past year will be collected for SPR001-naïve subjects. If a subject completed the final follow-up visit in Study SPR001-201 before the screening period for this study, any significant medical history and medications taken during the intervening period should be captured.

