## 4 STUDY DESIGN

### 4.1 Overall Design

This is a Phase 2 study of SPR001 for the treatment of classic CAH that will provide 12 weeks of open-label treatment to eligible subjects. To be eligible for this study, an individual must either have completed Study SPR001-201 or meet eligibility criteria for SPR001-naïve subjects (see [Section 5.2](#)). The expected duration of study participation for each subject is up to approximately 7 months. This includes a screening period of 12 weeks, a treatment period of 12 weeks, and a safety follow-up period of 30 days.

Initial subjects who enroll in this study will be treated with SPR001 at 400 mg QD during the treatment period. For subjects who enroll later on in this study, the dose strength may be increased or decreased (by no more than 2-fold) and/or the dose regimen may be adjusted (e.g., to BID dosing, a regimen being tested in Study SPR001-201). In general, subjects are expected to complete the study at the dose strength and on the dose regimen at which they started the study, unless they experience a clinically significant AE that would warrant a dose reduction.

An SRC will review the available safety, PK, and PD data from Study SPR001-201 Cohorts B/C/D and from this study on an ongoing basis and provide recommendations to the Sponsor, who will ultimately decide on any dosing adjustments in this study.

The Schedule of Activities is provided in [Section 1.3](#). Study visits will occur every 2 weeks during the treatment period and should be scheduled for the morning, to accommodate 8am laboratory assessments. Study visits for screening and at Day 1 (baseline), Week 4, Week 8, and Week 12 (end of treatment) will be conducted as outpatient clinic visits. Study visits at Week 2, Week 6, and Week 10 may be conducted as either outpatient clinic visits or in-home visits by qualified study personnel. A final safety follow-up outpatient clinic visit will occur 30 days after the last dose of study drug.

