## **8.2 Adverse Events and Serious Adverse Events**

### **8.2.1 Definition of Adverse Event**

An AE is any untoward medical occurrence in a clinical trial subject who has signed the informed consent form (ICF); the event need not necessarily have a causal relationship with the study drug. Examples of AEs include but are not limited to:

- Abnormal test results
- Clinically significant symptoms and signs
- Changes in physical examination findings
- Hypersensitivity
- Progression/worsening of underlying disease

A TEAE is an AE that is temporally associated with administration of study drug and is defined as an AE that occurs during or after administration of the first dose of study drug until 30 days after the final dose of study drug (safety follow-up visit). For AEs that occur on the date of the first dose of study drug, the time of onset (before or after intake of study drug) must be specified.

An abnormal test result should be reported as an AE if any of the following criteria are met:

- Test result is associated with accompanying symptoms
- Test result requires additional diagnostic testing or medical/surgical intervention
- Test result leads to a change in study drug dosing or study drug discontinuation, significant additional concomitant drug treatment, or other therapy
- Test result is considered to be an AE by the Investigator or Sponsor

Merely repeating an abnormal test, in the absence of any of the above conditions, does not constitute an AE. Any abnormal test result that is determined to be an error does not require reporting as an AE.

Diagnostic and therapeutic non-invasive and invasive procedures, such as surgery, should not be reported as AEs. However, the medical condition for which the procedure was performed should be reported if it meets the definition of an AE. For example, an acute appendicitis that

begins during the AE reporting period should be reported as the AE, and the resulting appendectomy should be recorded as treatment of the AE.

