6. CONSIDERATIONS FOR DATA ANALYSES AND HANDLING

All data from scheduled and unscheduled visits will be presented in the subject listings.

However, unless noted otherwise, only data from scheduled/windowed visits will be included in the summaries, statistical analysis, and calculation of derived parameters.

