6.6.4. Visit Windows

All assessments will be summarized using analysis windows.

The terminology of unscheduled will be applied to assessments that are outside an analysis window regardless, of the nominal label associated with the assessments in the EDC system.

The following visit windows will be used in the summary of clinical data.

Table 3: Analysis Visit Windows

Nominal Period/Visit	Start (days)	Stop (days)
Baseline	1	1
Week 2 (Day 15)	2	21
Week 4 (Day 29)	22	35
Week 6 (Day 43)	36	49
Week 8 (Day 57)	50	63
Week 10 (Day 71)	64	77
Week 12 (Day 85)	78	91
Week 16 (Day 112)	92	120

Safety Endpoints

The following windows summarize the definition of treatment-emergent.

Table 4: Analysis Windows for Safety Endpoints

Window	Start	Stop
Adverse events	Sign of ICF	30 days post last dose
Treatment-emergent Adverse events, ECGs and Labs	Post first dose	Last dose + 30 days
Prior Medications	Prior to first dose	First dose
Concomitant Medications	Post first dose	Last dose + 24 hours
Post Medications	Post last dose + 24 hours	NA

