14.3.3.1.1	Treatment-Emergent Adverse Events Overall Summary	Safety
14.3.3.1.2	Treatment-Emergent Adverse Events by Preferred Team	Safety
14.3.3.1.3	Treatment-Emergent Adverse Events by System Organ Class and Preferred Term	Safety
14.3.3.2	Treatment-Emergent Adverse Events by System Organ Class and Preferred Term and Severity	Safety
14.3.3.3.1	Drug-Related Treatment-Emergent Adverse Events by System Organ Class and Preferred Term	Safety
14.3.3.3.2	Drug-Related Treatment-Emergent Adverse Events by System Organ Class and Preferred Term and Severity	Safety
14.3.3.4.1	Serious Treatment-Emergent Adverse Events by System Organ Class and Preferred Term	Safety
14.3.3.4.2	Drug-Related Serious Treatment-Emergent Adverse Events by System Organ Class and Preferred Term	Safety
14.3.3.5.1	Treatment-Emergent Adverse Events Resulting On-Study Deaths	Safety
14.3.3.5.2	Deaths Within 28 Days	Safety
14.3.3.6.1	Treatment-Emergent Adverse Events Leading to Premature Study Drug Discontinuation	Safety
14.3.4.1.1.1	Hematology	Safety
14.3.4.1.1.2	Hematology: Shift from Baseline	Safety
14.3.4.1.2.1	Serum Chemistry	Safety
14.3.4.1.2.2	Serum Chemistry: Shift from Baseline	Safety
14.3.4.1.3	Urinalysis	Safety
14.3.5.1.1	Vital Signs: Diastolic Blood Pressure	Safety
14.3.5.1.2	Vital Signs: Systolic Blood Pressure	Safety
14.3.5.1.3	Vital Signs: Heart Rate	Safety
14.3.6.1	Concomitant Medications	Safety
14.3.7.1.1	Electrocardiogram Summary: HR	Safety
14.3.7.1.2	Electrocardiogram Summary: PR	Safety
14.3.7.1.3	Electrocardiogram Summary: QRS	Safety
14.3.7.1.4	Electrocardiogram Summary: QT	Safety
14.3.7.1.6	Electrocardiogram Summary: QTcF	Safety
14.3.7.2	Electrocardiogram Threshold Summary	Safety
14.3.7.3	Electrocardiogram Outlier Summary by Visit and Time Point	Safety
14.3.8.1	Hospital Anxiety and Depression Scale by Visit	Safety
14.3.8.2	Suicidal Ideation and Suicidal Behavior (C-SSRS) by Visit	Safety

Listings

Number	Title	Analysis Set
16.2.1.1	Study Disposition	Randomized
16.2.1.2	Discontinuations	Randomized
16.2.1.3	Inclusion And Exclusion Criteria	Randomized
16.2.1.4	Analysis Sets	Randomized
16.2.1.5.1	Randomization	Randomized
16.2.1.5.2	Subjects Receiving Incorrect Treatment	Randomized
16.2.1.7	Medical History	Randomized
16.2.2.1.1	Protocol Deviation Identified Prior To Database Lock By Site	Randomized
16.2.2.1.2	Protocol Deviation Identified Post Database Lock	Randomized
16.2.2.1.3	Major Analysis Protocol Deviations	Randomized

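### SAP Table 3 fixes the final safety visit at Day 112 with a stop at Day 120, so some protocol-compliant late visits leave the by-visit summaries; AEs with onset on last dose +31 to +37 are listed but not tabulated

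*SAP*

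**What the plan says.** **Timing of the visit.** Protocol 4.1: "A final safety follow-up outpatient clinic visit will occur 30 days after the last dose of study drug". Footnote 2 of the Schedule of Activities (Protocol 1.3, repeated in SAP 4.5) allows ± "7 days for the safety follow-up visit (Visit 9"). A compliant visit can therefore fall anywhere from last dose + 23 to last dose + 37.

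**By-visit window.** In SAP 6.6.4, Table 3, the row "Week 16 (Day 112") runs from Day 92 to Day 120. An assessment outside its window is called unscheduled, whatever its nominal label. SAP 6 then says that, unless noted otherwise, "only data from scheduled/windowed visits will be included in the summaries". The same section keeps all data, scheduled or not, in the listings.

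**Treatment-emergent window.** SAP 6.6.2 counts AEs by start date from first dose "until the last dose date/time plus the protocol defined follow-up period, 30 days" and puts only those events in tables. Table 4 gives the same stop to "Treatment-emergent Adverse events, ECGs and Labs". Protocol 8.2.1 has the same limit, worded "until 30 days after the final dose of study drug (safety follow-up visit").

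**AE recording.** SAP 6.6.2 records AEs through the final follow-up assessment, whereas the AE row of Table 4 ends 30 days after last dose.

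**The concern.** Safety is the primary objective. The follow-up visit is the scheduled off-drug check of clinical laboratory tests (liver chemistry included), HADS and the key hormones. Protocol 4.2 relies on the post-treatment period for safety follow-up and for analysis of any HPA-axis rebound.

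Two SAP rules do not fit the visit that the protocol describes. Table 3 is tied to a fixed study day, while the visit is tied to last dose. The treatment-emergent window closes on the target day of the visit, while the visit itself may come up to a week later. Protocol 8.2.1 treats 30 days and the follow-up visit as the same moment, which holds only if nobody uses the +7 allowance.

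The practical result is that where a finding appears can depend on which permitted day the subject attends. For example, Protocol 7.2.5 makes a HADS subscale score above 12 at any visit after baseline an AE of special interest. If such a score is first found and dated at a compliant visit on +34, it is an AE of special interest under the protocol but not treatment-emergent under the SAP. Nor can a late onset be presumed drug-free: Protocol 4.2 puts essentially complete elimination at 32 to 44 days, which begins after the window has closed.

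**Working it through.** **Inputs.** Visit target last dose + 30, window ±7 (Protocol 1.3 and 4.1). Week 12 visit on Day 85, window ±3 (Protocol 1.3). Dosing in the evening for 12 weeks (Protocol 6.1.2). Week 16 window Day 92 to 120, anchor Day 112 (SAP Table 3). Final n = 11 (SAP 4.3).

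**Assumption.** No document states the last dose as a study day. Eighty-four evening doses from Day 1 give a nominal last dose on Day 84. The range Day 81 to 88 is taken from the ±3 days around the Week 12 visit.

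**1. Reproducing Day 112 and Day 120.** Every other post-baseline row of Table 3 follows 7 × week + 1 (15, 29, 43, 57, 71, 85). That rule gives 7 × 16 + 1 = 113 for Week 16. Last dose + 30 gives 84 + 30 = 114. Only 7 × 16 gives 112. The stop day fits that anchor, since 112 + 7 = 119 is inside 120, but not the protocol's target, since 114 + 7 = 121.

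**2. Compliant days beyond Day 120.** Permitted days run from last dose + 23 to last dose + 37, which is 15 days.

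| Last dose | Target | Permitted range | Days after 120 |
|---|---|---|---|
| Day 81 | 111 | 104–118 | 0 of 15 |
| Day 82 | 112 | 105–119 | 0 of 15 |
| Day 83 | 113 | 106–120 | 0 of 15 |
| Day 84 | 114 | 107–121 | 1 of 15 |
| Day 85 | 115 | 108–122 | 2 of 15 |
| Day 86 | 116 | 109–123 | 3 of 15 |
| Day 87 | 117 | 110–124 | 4 of 15 |
| Day 88 | 118 | 111–125 | 5 of 15 |

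The latest last dose for which every permitted day is kept is 120 − 37 = Day 83. A visit exactly on target is inside the window in every row.

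**3. Weight of one visit.** If all 11 subjects attend, one relabelled visit is 1/11 = 9% of the Week 16 data.

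**4. Treatment-emergent window.** Days +31 to +37 are 7 of the 15 permitted days, whatever the last dose day. With a last dose on Day 84, +31 to +36 are Days 115 to 120. A visit then is inside the Week 16 by-visit window, but an AE with onset on that day is not treatment-emergent. On +37 (Day 121) it is outside both.

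**The case against.** The strongest reply is that the 30-day TEAE limit is the protocol's own, so the SAP sentence is no departure, and that a fixed 30 days gives every subject the same at-risk period. The first part is right. What remains is that the protocol's wording equates that limit with a visit that may come later, and that SAP 6.6.2 and Table 4 disagree on when AE collection ends.

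It is also fair to say that nothing is deleted. All data are listed, and non-treatment-emergent AEs have Listing 16.2.7.5. With 11 subjects and, in general, no inferential testing of AE rates, a reader can go through every line. The loss is from summary tables only.

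The Table 3 effect is small at the nominal schedule. SAP 4.2 describes dosing for up to 12 weeks, which ends on Day 84, and visits are meant to occur on their target days.

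Three stronger readings are tempting and are not supported:

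- A reader might multiply 7/15 by 11 and infer that about 5 subjects have final-visit findings reclassified. The figure of 5.1 is an expected number of late visits if attendance were even across the window. AEs are classified by onset, so an event that began by +30 and is reported at +37 still counts.
- A reader might infer that labs on +31 to +37 drop out because Table 4 names labs and ECGs. Labs are summarised by visit, and no table in the SAP index is titled as treatment-emergent labs or ECGs, so the reach of that row is unclear.
- A reader might take Table 14.3.3.5.2, "Deaths Within 28 Days", as a third cut-off that loses deaths. It is only a title with no stated anchor, and deaths also appear in the overall AE summary, Table 14.3.3.5.1 and Listing 16.2.7.4.

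**Conclusion.** The point holds as a window misalignment, limited in size. Table 3 takes its Week 16 anchor and stop from Day 112, not from last dose + 30, and so can relabel a compliant final safety visit as unscheduled. The exposure is 0 of 15 permitted days for a last dose on Days 81 to 83, 1 of 15 at the nominal Day 84 and 4 of 15 for Day 87. These figures rest on derived last dose days. How many of the 11 subjects are affected depends on attendance dates that the documents do not give.

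Separately, an AE with onset on +31 to +37, including an abnormality first found and dated at a compliant visit, is listed but not tabulated. That follows from a limit shared by both documents. The inconsistency lies between that limit, the ±7-day visit window and the SAP's statement that AEs are recorded through the final assessment.

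This does not undermine the safety evaluation. It is a wording defect in a small study whose primary objective is safety, and it is cheap to remove.

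**What to change.** 1. **SAP Table 3.** Define the Week 16/follow-up window relative to last dose, from +23 to +37 days, and correct the Day 112 label. A simpler alternative is to move the stop day from 120 to at least 124, but a last dose on Day 88 would need Day 125, so the relative definition is safer.
2. **SAP 6.6.2, 8.1 and Table 4, read with Protocol 8.2.1.** Reconcile them in one of two ways. Either end the treatment-emergent window at the later of last dose + 30 days and the actual follow-up visit, with a maximum of +37, or keep 30 days and tabulate +31 to +37 onsets separately. The second option leaves the protocol's limit untouched.
3. **Table 4.** State which outputs, if any, apply the +30 stop to labs and ECGs, and align the AE row with the recording period in 6.6.2.

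The cost is a few lines of SAP text. Under the first option in item 2, a few late and possibly unrelated AEs are counted and the length of follow-up varies slightly between subjects.
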